13.4 Publication, Disclosure, and Clinical Trial Registration Policy

13.4.1 Publication and Disclosure

The investigator is obliged to provide the Sponsor with complete test results and all data derived by the investigator from the study. During and after the study, only the Sponsor may make study information available to other study investigators or to regulatory agencies, except as required by law or regulation. Except as otherwise allowable in the clinical study site agreement, any public disclosure (including publicly accessible websites) related to the protocol or study results is the sole responsibility of the Sponsor.

The Sponsor may publish any data and information from the study (including data and information generated by the investigator) without the consent of the investigator. The investigator or sub-investigator needs to obtain a prior written approval from the Sponsor to publish any information from the study externally such as to a professional association.

13.4.2 Clinical Trial Registration

In order to ensure that information on clinical trials reaches the public in a timely manner and to comply with applicable laws, regulations and guidance, Takeda will, at a minimum register all interventional clinical trials it sponsors anywhere in the world on ClinicalTrials.gov and/or other publicly accessible websites before start of study, as defined in Takeda Policy/Standard. Takeda contact information, along with investigator's city, state (for Americas investigators), country, and recruiting status will be registered and available for public viewing.

13.4.3 Clinical Trial Results Disclosure

Takeda will post the results of clinical trials on ClinicalTrials.gov or other publicly accessible websites, as required by Takeda Policy/Standard, applicable laws and/or regulations.

13.5 Insurance and Compensation for Injury

Each subject in the study must be insured in accordance with the regulations applicable to the study site where the subject is participating. If a local underwriter is required, then the Sponsor or Sponsor's designee will obtain clinical study insurance against the risk of injury to study subjects. Refer to the study site agreement regarding the Sponsor's policy on subject compensation and treatment for injury. If the investigator or sub-investigator has questions regarding this policy, he or she should contact the Sponsor or Sponsor's designee.

14.0 ADMINISTRATIVE AND REFERENCE INFORMATION

14.1 Administrative Information

14.1.1 Study Contact Information

A separate contact information list (Protocol Annex 1) will be provided to the study site.

14.1.2 Investigator Agreement

A separate agreement will be provided to the study site.

14.1.3 Study-Related Responsibilities

A separate contact information list (Protocol Annex 1) will be provided to the study site.

14.1.4 List of Abbreviations

Term	Definition
ACE	angiotensin converting enzyme
AE	adverse event
ALT	alanine aminotransferase
ARB	angiotensin II receptor blocker
AST	aspartate aminotransferase
BMI	body mass index
CKD	chronic kidney disease
eCRF	electronic case report form
FDA	Food and Drug Administration
GCP	Good Clinical Practice
GGT	gamma-glutamyl transpeptidase
HBsAg	hepatitis B surface antigen
HCV	hepatitis C virus
HIV	human immunodeficiency virus
ICH	International Council for Harmonisation of Technical Requirements for Pharmaceuticals for Human Use
INR	international normalized ratio
MedDRA	Medical Dictionary for Regulatory Activities
MHRA	Medicines and Healthcare products Regulatory Agency
PMDA	Pharmaceuticals and Medical Devices Agency
SAE	serious adverse event
SAP	statistical analysis plan
SUSAR	suspected unexpected serious adverse reaction
TEAE	treatment emergent AE

15.0 DATA HANDLING AND RECORDKEEPING

The full details of procedures for data handling will be documented in the Data Management Plan. AEs, medical history, and concurrent conditions will be coded using the MedDRA. Drugs will be coded using the World Health Organization Drug Dictionary.

15.1 eCRFs

Completed eCRFs are required for each subject who signs an informed consent.

The Sponsor or its designee will supply investigational sites with access to eCRFs. The Sponsor will make arrangements to train appropriate site staff in the use of the eCRF. These forms are used to transmit the information collected in the performance of this study to the Sponsor and regulatory authorities. eCRFs must be completed in English. Data are transcribed directly onto eCRFs.

After completion of the entry process, computer logic checks will be run to identify items, such as inconsistent dates, missing data, and questionable values. Queries may be issued by Takeda personnel (or designees) and will be answered by the study site.

Corrections are recorded in an audit trail that captures the old information, the new information, identification of the person making the correction, the date the correction was made, and the reason for change. Reasons for significant corrections should additionally be included.

The investigator must review the eCRFs for completeness and accuracy and must e-sign the appropriate eCRFs as indicated. Furthermore, the investigator must retain full responsibility for the accuracy and authenticity of all data entered on the eCRFs.

The following data will not be recorded into the eCRFs:

- Laboratory results
- Measurement results of drug concentrations

After the lock of the clinical study database, any change of, modification of, or addition to the data on the eCRFs should be made by the investigator or sub-investigator with use of change and modification records of the eCRFs. The investigator must review the data change for completeness and accuracy, and must e-sign.

eCRFs will be reviewed for completeness and acceptability at the study site during periodic visits by study monitors. The Sponsor or its designee will be permitted to review the subject's medical and hospital records pertinent to the study to ensure accuracy of the eCRFs. The completed eCRFs are the sole property of the Sponsor and should not be made available in any form to third parties, except for authorized representatives of appropriate governmental health or regulatory authorities, without written permission of the Sponsor.

15.2 Record Retention

The investigator or the head of the study site agrees to keep the records stipulated in Section 15.1 and those documents that include (but are not limited to) the study-specific documents, the identification log of all participating subjects, medical records, all original signed and dated

informed consent forms, electronic copy of eCRFs, including the audit trail, and detailed records of drug disposition to enable evaluations or audits from regulatory authorities, the Sponsor or its designees. The investigator and the head of the study site are required to retain relevant essential documents until the day specified as 1 or 2 below, whichever comes later. However, if the Sponsor requests a longer time period for retention, the head of the study site should discuss how long and how to retain those documents with the Sponsor.

1. The day on which marketing approval for the study drug is obtained (or the day 3 years after the date of notification in the case that the investigation is discontinued.)
2. The day 3 years after the date of early termination or completion for the study.

In addition, the investigator and the head of the study site should retain the relevant essential documents until the receipt of a Sponsor-issued notification that states the retention is no longer required.

17.0 APPENDICES

Appendix A Responsibilities of the Investigator

1. Conduct the appropriate study in accordance with the protocol and GCP considering the rights, safety and wellbeing of human subjects.
2. When a part of the important activities related to the study are delegated to a sub-investigator or the study collaborator, prepare the lists of activities to be delegated and responsible personnel, submit the lists to the head of the study site in advance to get them accepted.
3. Prepare a written informed consent form and other written information, and update as appropriate.
4. Confirm the contents of the clinical study agreement.
5. Provide necessary information on the protocol, medications and responsibilities of individual personnel to the sub-investigator and study collaborator, and provide guidance and supervision.
6. Screen subjects who meet the requirements of the protocol, provide the explanation of the study in writing and obtain the written consent.
7. Assume responsibility for all the medical judgement related to the study.
8. Ensure in collaboration with the head of the study site that sufficient medical care for all clinically significant AEs related to the study are provided to subjects throughout and beyond the period when subjects participate in the study, upon obtaining consent from the subject.
9. If a subject consults other medical institution or other department, notify the physician of the medical institution or department of the subject's participation in the study, as well as the end and termination of the study in writing, and document such records.
10. In case of urgent report of a SAE, immediately notify the head of the study site and the Sponsor in writing.
11. Determine the need of emergency key code blinding of a subject in case of emergency. [For double-blinded studies only.]
12. Prepare correct and complete eCRFs, and submit them to the Sponsor with electronic signature.
13. Check and confirm the contents of eCRFs prepared by the sub-investigator or transcribed from the source data by the study collaborator, and submit them to the Sponsor with electronic signature.
14. Discuss any proposal from the Sponsor including update of the protocol.
15. Notify the head of the study site of the end of the study in writing.

Appendix B Acceptable Time Window for Study Procedure

Acceptable time window for safety examination/test/observations (Periods 1 and 2)

As per the Protocol		Acceptable Time Window
Tests/Observation Item	Designated Time Point	
Physical examination	Screening	From 28 days to 2 days before the study drug administration
	Day -1	same as on the left
	Before the study drug administration	From waking-up to immediately before the study drug administration
	4 hours postdose	±30 minutes
	24 and 48 hours postdose	±120 minutes
	Follow-up examination (Day 6)	±1 day
Height	Screening	From 28 days to 2 days before the study drug administration
Weight	Screening	From 28 days to 2 days before the study drug administration
	Before the study drug administration	From waking-up to immediately before the study drug administration
	48 hours postdose	±120 minutes
	Follow-up examination (Day 6)	±1 day
Vital signs (Sitting blood pressure, sitting pulse, and body temperature)	Screening	From 28 days to 2 days before the study drug administration
	Before the study drug administration	From waking-up to immediately before the study drug administration
	4 hours postdose	±30 minutes
	24 and 48 hours postdose	±120 minutes
	Follow-up examination (Day 6)	±1 day
Resting 12-lead ECG	Screening	From 28 days to 2 days before the study drug administration
	Before the study drug administration	From waking-up to immediately before the study drug administration
	48 hours postdose	±120 minutes
	Follow-up examination (Day 6)	±1 day
Laboratory tests (Blood)	Screening	From 28 days to 2 days before the study drug administration
	Before the study drug administration	From waking-up to immediately before the study drug administration
	24 and 48 hours postdose	±120 minutes
	Follow-up examination (Day 6)	±1 day

As per the Protocol		Acceptable Time Window
Tests/Observation Item	Designated Time Point	
Laboratory tests (Urine)	Screening	From 28 days to 2 days before the study drug administration
	Before the study drug administration	From waking-up to immediately before the study drug administration
	24 and 48 hours postdose	From waking-up to +120 minutes
	Follow-up examination (Day 6)	±1 day

Acceptable time window for PK blood sampling (Periods 1 and 2)

As per the Protocol		Acceptable Time Window
Tests/Observation Item	Designated Time Point	
Plasma drug concentration	Before the study drug administration	From waking-up to immediately before the study drug administration
	0.5, 1, 1.5, 2, 2.5, 3, 3.5, 4, 5, 6, 8, and 12 hours postdose	±5 minutes
	16, 24, and 48 hours postdose	±15 minutes

Total blood sampling volume for an individual subject is shown below.

Sample Type	Volume	Number of Samples		Total Volume (mL)	
		Screening	Period 1	Period 2	
Clinical laboratory tests samples	16 mL at Screening/ 10 mL at other time points	1	4	4	96
PK samples for TAK-536	3 mL	0	16	16	96
Total blood sampling volume					192

A Randomized, Open-Label, Cross-over Phase 1 Study to Evaluate the Food Effect of Single Oral Dose of
TAK-536 Pediatric Formulation in Healthy Adult Male Subjects

ELECTRONIC SIGNATURES

Signed by	Meaning of Signature	Server Date (dd-MMM-yyyy HH:mm 'UTC')
PPD	Clinical Approval	06-Mar-2018 00:40 UTC

### **3.0 LIST OF ABBREVIATIONS**

Term	Definition
ACE	angiotensin converting enzyme
AE	adverse event
ALT	alanine aminotransferase
ARB	angiotensin II receptor blocker
AST	aspartate aminotransferase
BMI	body mass index
CKD	chronic kidney disease
eCRF	electronic case report form
FDA	Food and Drug Administration
GCP	Good Clinical Practice
GGT	gamma-glutamyl transpeptidase
HBsAg	hepatitis B surface antigen
HCV	hepatitis C virus
HIV	human immunodeficiency virus
ICH	International Council for Harmonisation of Technical Requirements for Pharmaceuticals for Human Use
INR	international normalized ratio
MedDRA	Medical Dictionary for Regulatory Activities
MHRA	Medicines and Healthcare products Regulatory Agency
PMDA	Pharmaceuticals and Medical Devices Agency
SAE	serious adverse event
SAP	statistical analysis plan
SUSAR	suspected unexpected serious adverse reaction
TEAE	treatment emergent AE

## **4.0 OBJECTIVES**

### **4.1 Primary Objectives**

To assess the food effect on the pharmacokinetics (PK) following single oral administration of TAK-536 pediatric formulation in Japanese healthy adult male subjects

### **4.2 Secondary Objectives**

To assess the food effect on the safety of a single oral administration of TAK-536 pediatric formulation in Japanese healthy adult male subjects

### **4.3 Additional Objectives**

Not applicable in this study.

### **4.4 Study Design**

This is an open-label, 2×2 crossover study to assess the food effect on the PK and safety of a single oral dose of TAK-536 pediatric formulation in Japanese healthy adult male subjects under fasted or fed conditions in the morning.

The dosage, treatment condition, and number of subjects are shown in Table 4.a. Each subject will receive the study drug under one of the following treatment conditions in each period.

1. One sachet of TAK-536 10 mg granules (TAK-536 10 mg) will be administered orally with 200 mL of water in the morning under fasted condition (fasted overnight for at least 10 hours prior to the study drug administration).
2. One sachet of TAK-536 10 mg granules (TAK-536 10 mg) will be administered orally with 200 mL of water in the morning under fed condition (at 30 minutes after starting breakfast).

**Table 4.a Dosage, Treatment Condition, and Number of Subjects**

Sequence	Number of subjects	Dose of TAK-536	Regimen	
			Period 1	Period 2
A	6	TAK-536 10 mg Granules (TAK-536 10 mg)	Single oral dose under fasted condition	Single oral dose under fed condition
B	6	TAK-536 10 mg Granules (TAK-536 10 mg)	Single oral dose under fed condition	Single oral dose under fasted condition

Subjects will be screened for enrollment from 4 weeks (28 days) to 2 days (the day before admission) before the study drug administration (Day -28 to Day -2) in Period 1. Subjects will be admitted to the study site on the day before the study drug administration (Day -1) in both Periods 1 and 2, and will be hospitalized under medical supervision for 4 days (until 48 hours after the study drug administration). They will undergo daily examinations and observations from the day before the study drug administration (Day -1) during their

hospitalization according to the study schedule specified in the protocol section 3.0, and will be discharged from the study site on Day 3 after confirmation of safety by the investigator or sub-investigator. Subjects will return to the study site for follow-up examinations on Day 6. At least 6-day washout interval will be placed between the study drug administrations in Periods 1 and 2.

Subjects will visit the study site 5 times, including the visit for screening examinations, in this study. They will be hospitalized for a total of 8 days in Periods 1 and 2 (A schematic of the study design is shown in Figure 4.b).

The examinations scheduled on the day before the study drug administration (Day -1) in Period 2 can be replaced with the follow-up examinations (Day 6) in Period 1 if they are scheduled on the same day. If this is the case, the subject will visit the study site 4 times in this study.

**Figure 4.b Schematic of Study Design**

Element	Screening		Treatment (TAK-536 10 mg pediatric formulation) Period 1 and Period 2*				
Day	Day -28 to Day -2	Day -1	Day 1	Day 2	Day 3		Day 6
	Visit	Hospitalization					Visit
Content	Informed consent Screening	Admission	Study drug administration		Discharge		Follow-up examination
						...	

\*: There will be at least 6-day washout interval between the study drug administrations in Periods 1 and 2. The examinations scheduled on the day before the study drug administration (Day -1) in Period 2 can be replaced with the follow-up examinations (Day 6) in Period 1, provided that they are scheduled on the same day.

## **5.0 ANALYSIS ENDPOINTS**

### **5.1.1 Primary Endpoints**

PK: Plasma concentrations and PK parameters of unchanged TAK-536 ( $C_{max}$ ,  $t_{max}$ ,  $AUC_{last}$ ,  $AUC_{\infty}$ ,  $t_{1/2z}$ , MRT,  $\lambda_z$ , CL/F, and  $V_z/F$ )

### **5.1.2 Secondary Endpoints**

Safety: Adverse events (AEs), vital signs (sitting blood pressure, sitting pulse rate, and body temperature), weight, laboratory test results (hematology, serum chemistry, and urinalysis), and resting 12-lead ECGs

## **6.0 DETERMINATION OF SAMPLE SIZE**

A total of 12 subjects (6 per sequence)

[Sample size justification]

A total of 12 subjects, with 6 subjects in each sequence, were considered sufficient sample size to evaluate the PK and safety of TAK-536. The sample size is not based on statistical considerations.

## 7.0 METHODS OF ANALYSIS AND PRESENTATION

### 7.1 General Principles

#### 7.1.1 Study Definitions

- Treatment-emergent adverse event (TEAE): Adverse events that occurred after the start of the study drug administration
  - \* Among the TEAEs, those that occurred from the start of the study drug administration in Period 1 to before the start of the study drug administration in Period 2 are deemed as “TEAEs that occurred in Period 1” and those that occurred after the start of the study drug administration in Period 2 as “TEAEs that occurred in Period 2.”
- Pretreatment event(PTE):Adverse events that occurred after obtaining the consent but before the start of the study drug administration
- Descriptive statistics: Number of subjects, mean, standard deviation, maximum, minimum, and quartiles
- Coefficient of variation (CV)(%): Standard deviation / Mean x 100
- QTcF interval: QT interval corrected with Fridericia’s correction
- Treatment conditions:
  - Single oral dose under fasted condition
  - Single oral dose under fed condition
- Treatment group:
  - A (Single oral dose under fasted condition → Single oral dose under fed condition)
  - B (Single oral dose under fed condition → Single oral dose under fasted condition)

#### 7.1.2 Definition of Study Days

- Total Study Time in each time interval (hour): Time and date of test/observation/assessment - Time and date of start of study drug administration in each time interval (rounded to the fourth decimal place)

#### 7.1.3 Definition of Study Visit Windows

For items of examinations, observations, and assessments described below, evaluable data (i.e., non-missing data) will be handled according to the following rules.

Evaluable data within the visit window will be used. If more than one evaluable data exist within the same visit window, the examinations, observations, and assessments with the closest Study Time to the scheduled Study Time will be used. If there are two evaluable equidistant to the scheduled Study Time, the later data will be used. The size of difference from the Study Time will be determined based on the total Study Time in each time interval (hour).

For items from examinations, observations, and assessments other than those described below, evaluable data will be handled as data at the corresponding visit based on the visits specified in the case report form. However, among the visits specified in the case report form, if the follow-up examination in Period 1 (Day 6) and the examination on the day before the study drug administration (Day -1) in Period 2 were conducted on the same day and only the evaluable data exists from either the follow-up examination (Day 6) for Period 1 or the day before the study drug administration (Day -1) for Period 2, that data will be handled though it were obtained at both visits.

**Table 7.a Visit Window**

**Plasma drug concentration**

Visit	Scheduled Study Time	Total Study Time in each time interval (hour)
Predose	Study Time (hour): 0	-5.000 - 0.000
0.5 Hour Postdose	Study Time (hour): 0.5	0.417 - 0.583
1 Hour Postdose	Study Time (hour): 1	0.917 - 1.083
1.5 Hours Postdose	Study Time (hour): 1.5	1.417 - 1.583
2 Hours Postdose	Study Time (hour): 2	1.917 - 2.083
2.5 Hours Postdose	Study Time (hour): 2.5	2.417 - 2.583
3 Hours Postdose	Study Time (hour): 3	2.917 - 3.083
3.5 Hours Postdose	Study Time (hour): 3.5	3.417 - 3.583
4 Hours Postdose	Study Time (hour): 4	3.917 - 4.083
5 Hours Postdose	Study Time (hour): 5	4.917 - 5.083
6 Hours Postdose	Study Time (hour): 6	5.917 - 6.083
8 Hours Postdose	Study Time (hour): 8	7.917 - 8.083
12 Hours Postdose	Study Time (hour): 12	11.917 - 12.083
16 Hours Postdose	Study Time (hour): 16	15.750 - 16.250
24 Hours Postdose	Study Time (hour): 24	23.750 - 24.250
48 Hours Postdose	Study Time (hour): 48	47.750 - 48.250

## **7.2 Analysis Sets**

- Pharmacokinetic (PK) Analysis Set: All subjects who received the study drug, completed the minimum protocol-specified procedures without any major protocol deviations, and were evaluable for pharmacokinetics
  - Any subject who meets the following criteria will be excluded from this analysis set:
    - 1) Deviations of protocol entry criteria
      - Deviations of inclusion criteria
        - Inclusion criteria 3, 4, and 5
        - Deviations of exclusion criteria
          - Exclusion criteria 2, 4, 6, 7, 8, 9, 10, 11, and 17

- 2) Deviations related to treatment procedure or dose
  - Deviations related to dose
    - Deviations of dosage

Subjects who received a dose of the study drug other than the doses specified in the protocol
    - Deviations of regimen
      - Deviations of dosing interval (number of days for washout)

Subjects who received the study drug in Period 2 without undergoing a washout period of more than 6 days after the study drug administration in Period 1
      - Deviations of dosing conditions

Subjects who did not orally receive a single dose of any study drug under treatment conditions specified in that treatment period
- 3) Deviations concerning excluded medication or therapy
  - Deviations concerning concomitant medications
    - Administration of excluded medication

Subjects who consumed drugs (prescribed or over-the-counter drugs) described in Table 7.a “Excluded Medications, Supplements, and Dietary Products” listed in the protocol section 7.3 within the given time
- 4) Deviations concerning pharmacokinetic measurements
  - Plasma drug concentration
    - No conduct/missing of examinations and assessments concerning pharmacokinetic variables

Subjects whose plasma drug concentration data of TAK-536 was missing or not used at more than 1 visit
- 5) Others
  - Matters of subject management
    - Matters concerning foods and beverages
      - Subjects who consumed meals other than the provided meals during hospitalization
      - Subjects who consumed meals within 10 hours before the study drug administration
      - Subjects who consumed meals within 4 hours after the study drug administration
      - Subjects who consumed beverages other than the drink provided as a part of breakfast (under fed condition) and water (200 mL)

taken with the study drug from 1 hour before to 4 hours after the study drug administration

Subjects who consumed foods described in Table 7.a “Excluded Medications, Supplements, and Dietary Products” listed in the protocol section 7.3 within the given time

Matters concerning smoking

Subjects who smoked during hospitalization

Matters concerning body position

Subjects who took a supine position for 4 hours after the study drug administration, unless it was required for examination.

- Safety Analysis Set: All subjects who received the study drug

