6.0 TRIAL DESIGN AND DESCRIPTION

6.1 Trial Design

This is an open-label, 2×2 crossover study to assess the food effect on the PK and safety of a single oral dose of TAK-536 pediatric formulation in Japanese healthy adult male subjects under fasted or fed condition in the morning.

The dosage, treatment condition, and number of subjects are shown in [Table 6.a](#). Each subject will receive the study drug under one of the following treatment conditions in each period.

1. One sachet of TAK-536 10 mg granules (TAK-536 10 mg) will be administered orally with 200 mL of water in the morning under fasted condition (fasted overnight for at least 10 hours prior to study drug administration).
2. One sachet of TAK-536 10 mg granules (TAK-536 10 mg) will be administered orally with 200 mL of water in the morning under fed condition (at 30 minutes after starting breakfast).

Table 6.a Dosage, Treatment Condition, and Number of Subjects

Sequences	Number of Subjects	Dose of TAK-536	Regimen	
			Period 1	Period 2
A	6	TAK-536 10 mg Granules (TAK-536 10 mg)	Single oral dose under fasted condition	Single oral dose under fed condition
B	6	TAK-536 10 mg Granules (TAK-536 10 mg)	Single oral dose under fed condition	Single oral dose under fasted condition

Subjects will be screened for enrollment from 4 weeks (28 days) to 2 days (the day before admission) before the study drug administration (Day -28 to Day -2) in Period 1. Subjects will be admitted to the study site on the day before the study drug administration (Day -1) in both Periods 1 and 2, and will be hospitalized under medical supervision for 4 days (until 48 hours after the study drug administration). They will undergo daily examinations and observations from the day before the study drug administration (Day -1) during their hospitalization according to the study schedule specified in [Section 3.0](#), and will be discharged from the study site on Day 3 after confirmation of safety by the investigator or sub-investigator. Subjects will return to the study site for follow-up examinations on Day 6. At least 6-day washout interval will be placed between the study drug administrations in Periods 1 and 2.

Subjects will visit the study site 5 times, including the visit for screening examinations, in this study. They will be hospitalized for a total of 8 days in Periods 1 and 2 (refer to [Section 2.0](#) for a schematic of the study design).

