The examinations scheduled on the day before the study drug administration (Day -1) in Period 2 can be replaced with the follow-up examinations (Day 6) in Period 1, if they are scheduled on the same day. If this is the case, the subject will visit the study site 4 times in this study.

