6.2.4 Rationale for Washout Period

When a single oral dose of TAK-536 10 mg was administered under fasted condition to Japanese healthy adult subjects, plasma concentration of unchanged TAK-536 was 9 ng/mL at 72 hours after the administration in the subject with the highest plasma TAK-536 level. It was assumed that the plasma unchanged TAK-536 level would be below the lower limit of quantification (<1 ng/mL) at 6 days (3 days after the time point of C_{max}) after the administration based on the half-life of TAK-536 (about 13 hours). The Japanese Guideline for Bioequivalence Studies of Generic Products [12] recommends that there should be a washout period at least 5 times longer than the apparent half-life of the investigational drug between the two treatments to be compared within subjects. Thus, the washout period in this study was set as 6 days (144 hours), which is more than 5 times longer than the apparent elimination half-life of TAK-536.

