#### *7.3.4.2 Analysis Sets*

Analysis Set:	All Subjects Who Were Eligible for Randomization
Analysis Variable(s):	Handling of Subjects in Analysis Sets [Categories are based on the specifications in the List of Subject Evaluability Assignments]
	Inclusion/Exclusion of Analysis Set
	Safety Analysis Set [Included]
	PK Analysis Set [Included]
Analysis Method(s):	
The following summaries will be provided by treatment group for (1), and by treatment group and by combining the treatment groups for (2).
 
For (1), a subject who has several categories will be counted once in each appropriate category.
 
(1) Frequency distributions for handling of cases in each analysis set
 
(2) Frequency distributions for number of cases included in each analysis set

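### SAP 7.2 drops from the PK set any subject without a washout of more than 6 days, although the protocol and SAP 4.4 permit exactly 6 days

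*SAP*

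**What the plan says.** **Protocol.** Section 6.1 states: "At least 6-day washout interval will be placed between the study drug administrations in Periods 1 and 2". The study summary, the schematic and the schedule of procedures set the same inclusive minimum. Section 6.2.4 gives the reasoning and says that "the washout period in this study was set as 6 days (144 hours", in brackets as the hour equivalent. Section 6.1 also allows the two visits to be merged: the Day -1 examinations "in Period 2 can be replaced with the follow-up examinations (Day 6) in Period 1" when both fall on one day, which reduces the visits from 5 to 4. Appendix B gives the Day 6 follow-up a window of ±1 day.

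**SAP.** Section 4.4 repeats the inclusive minimum and the merged-visit option. Section 7.1.3 contains a data rule for when the two visits "were conducted on the same day and only the evaluable data exists from either the follow-up examination (Day 6) for Period 1" or from the Period 2 Day -1 visit. Section 7.2, under the heading "Deviations of dosing interval (number of days for washout", then excludes from the PK analysis set subjects who received Period 2 drug "without undergoing a washout period of more than 6 days after the study drug administration in Period 1". Section 7.13 says the planned analysis does not differ from the protocol's.

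**The concern.** The protocol minimum includes 6 days and the SAP exclusion rule does not allow it. A subject dosed exactly 6 days apart therefore complies with the protocol and with SAP 4.4, yet counts as a dosing-interval deviation under SAP 7.2. No reason is given for a stricter cut, and SAP 7.13 declares no change.

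The PK analysis set is the only set used for the concentration and parameter summaries and for the food-effect ANOVA (SAP 7.9.1.1 to 7.9.1.3). A subject wrongly dropped is lost from the primary analysis. There is little slack: the 12 subjects have no statistical justification (Protocol 11.3), and Protocol 7.8 does not replace anyone who discontinues after Period 1 dosing. If membership is left to interpretation in an open-label study, it may be settled after concentrations are known.

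**Working it through.** **1. The protocol's own washout figures (Protocol 6.2.4).** Inputs: washout 6 days; half-life about 13 h; 9 ng/mL at 72 h in the subject with the highest level, fasted; quantification limit 1 ng/mL.

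- 6 × 24 = 144 h, as stated.
- 144 / 13 = 11.1 half-lives, against a required 5 × 13 = 65 h.
- Concentration at 144 h: 9 × 2^(−(144 − 72)/13) = 9 × 2^(−72/13) = 0.19 ng/mL, below 1 ng/mL.
- Sensitivity: 0.06 ng/mL at a half-life of 10 h and 0.74 ng/mL at 20 h. The value reaches 1 ng/mL at 72 / log2(9) = 22.7 h.

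The protocol's conclusion is reproduced. These are fasted data, and no fed-state value is given. On these figures, nothing in the documents supports a longer cut than the protocol's.

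**2. Which schedules give exactly 6 days.** Number days from Period 1 dosing as Day 1. The interval is the Period 2 dosing day on that numbering minus 1, and dosing is the day after admission.

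| Follow-up | Period 2 admission | Period 2 dose | Interval | Protocol and SAP 4.4 | SAP 7.2 |
|---|---|---|---|---|---|
| Day 6, merged | Day 6 | Day 7 | 6 days | met | excluded |
| Day 7, merged | Day 7 | Day 8 | 7 days | met | kept |
| Day 5, merged | Day 5 | Day 6 | 5 days | not met | excluded |
| Day 5, separate | Day 6 | Day 7 | 6 days | met | excluded |
| Day 6, separate | Day 7 or later | Day 8 or later | 7 days or more | met | kept |

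The rules conflict in the first and fourth rows. The first is the merged visit on its nominal day. The fourth uses the ±1 day window of Appendix B.

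**3. Number affected.** If k of 12 subjects are dosed exactly 6 days apart, SAP 7.2 read literally leaves 12 − k in the PK set from this criterion alone. The protocol's minimum leaves 12. The documents do not say which schedule the site uses, so k runs from 0 to 12.

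**4. Cost in precision for a partial loss.** Assume the standard 2×2 crossover analysis with within-subject error, and sequences that stay balanced. The 90% half-width on the log scale is t(0.95, n − 2) × σ_w × √(2/n). The within-subject SD σ_w cancels in the comparison with n = 12.

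| n | t × √(2/n) | Relative to 12 |
|---|---|---|
| 12 | 0.740 | 1.00 |
| 10 | 0.832 | 1.12 |
| 8 | 0.972 | 1.31 |
| 6 | 1.231 | 1.66 |

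As an illustration, take a true ratio of 1 and a within-subject CV of 20% (an assumption; the documents give none). The interval for the fed/fasted ratio is 0.864 to 1.158 with 12 subjects and 0.784 to 1.276 with 6. At a CV of 15% the two intervals are 0.895 to 1.117 and 0.832 to 1.202; at 30% they are 0.805 to 1.243 and 0.697 to 1.435. With k = 12 there is no primary analysis.

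**5. Unit.** The SAP heading counts days, while Protocol 6.2.4 also gives hours. Counted by the clock, a subject dosed a few minutes earlier or later in Period 2 than in Period 1 falls on one side or the other of 144 h. Counted in days, he does not.

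**The case against.** The strongest reply is that this is loose wording with little likely effect.

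- **The base plan is unaffected.** Protocol 6.1 and SAP 4.4 describe 5 visits. On nominal days that gives 7 days or more and loses no one. This stands, and it makes 0 to 12 a bound and not a forecast. The merged visit is nevertheless written into both documents, and the SAP has a data rule for it.
- **The context suggests 6 days or more was meant.** The PK set is defined by the absence of major protocol deviations, SAP 4.4 has the inclusive minimum, and SAP 7.13 declares no change. Another item in the same list, on meals in the 10 hours before dosing, has no fasted-condition qualifier and cannot be applied literally either. The inference about intent is reasonable, but nothing in the SAP states it, and the text says such subjects will be excluded.
- **Another document may settle it.** SAP 7.3.4.2 says "Categories are based on the specifications in the List of Subject Evaluability Assignments". That list is not among the documents reviewed, and the SAP gives it no stated power to override 7.2.
- **The data would still be reported.** Individual concentration plots and parameter listings cover everyone who entered the treatment period (SAP 7.9.1.4 and 7.9.1.5), and the safety set is untouched. This is correct, and the loss could be reversed by re-analysis. The prespecified primary result would still omit these subjects.
- **The unit is already days.** The SAP heading does point that way, so this part is the smaller one.

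**Conclusion.** The concern holds. SAP 7.2 contradicts Protocol 6.1 and 6.2.4 and SAP 4.4 at an interval of exactly 6 days, which both documents allow for. Taken as written, it would remove compliant subjects from the primary PK analysis.

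The size depends wholly on scheduling: no loss if every interval is 7 days or longer, and loss of the entire PK set if the whole cohort is dosed exactly 6 days apart. Between those limits, the widening factors of 1.12, 1.31 and 1.66 assume balanced losses and the standard crossover error term. The conclusion rests on the literal text of SAP 7.2. The carry-over figures show only that the protocol's own argument gives no ground for the stricter cut, with the caveat that they come from fasted subjects.

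**What to change.** Before database lock, reconcile the dosing-interval item in SAP 7.2 with Protocol 6.1 and 6.2.4 and SAP 4.4, so that no subject dosed at an interval the protocol permits is excluded on this ground. In the same item, state whether the interval is counted in days or in hours, consistently with the protocol. Check that the List of Subject Evaluability Assignments follows the reconciled rule.

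The cost is one phrase and one short sentence in the SAP. Study conduct and data collection do not change.
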